5.3.3.2 Additional Efficacy and Health Outcome Variables

Secondary Endpoints (with hierarchical analysis)

- ON time without troublesome dyskinesia as measured by the PD Diary
- PDQ-8 Summary Index
- CGI-C
- UPDRS Part II Score
- OFF time as measured by PD Diary
- UPDRS Part III Score

Additional Efficacy Endpoints are:

- UDysRS Historical Score, Objective Score and Parts 1 through 4 Scores
- ON time with troublesome dyskinesia and ON time without dyskinesia as measured by PD Diary
- mAIMS

Additional Health Outcome Endpoints:

• King's PD Pain Scale

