LCIG is delivered to the proximal small intestine through a percutaneous endoscopic gastrostomy with jejunal extension tube (PEG-J). The LCIG is dispensed in medication cassette reservoirs. The contents of the medication cassette reservoir are delivered via continuous administration by an infusion pump as illustrated in Figure 1. Efficacy of upper-intestinal administration of LCIG has been demonstrated in Phase 3 studies. In the pivotal Phase 3 study (Study S187-3-001/Study S187-3-002), compared to Levodopa-Carbidopa Immediate Release (LC-IR), LCIG significantly improved "Off" time (LS Mean difference = -1.91 hours, P = 0.0015) and "On" time without troublesome dyskinesia ("On" time without dyskinesia + "On" time with non-troublesome dyskinesia, LS Mean difference = 1.86 hours, P = 0.0059) at Week 12. At Week 12, compared with LC-IR, LCIG treatment significantly decreased the percentage of the waking day in the "Off" state and significantly increased the percentage of waking day in the "On" state without troublesome dyskinesia. LCIG treatment also produced a significantly greater change from baseline in "On" time without dyskinesia compared to LC-IR. Most adverse events were transient and were mild or moderate in intensity and were generally associated with the PEG-J procedure and its complications. The most common adverse events were complication of device insertion (56.8%), abdominal pain (51.4%), nausea (29.7%), procedural pain (29.7%), constipation (21.6%) and incision site erythema $(18.9\%)^{21}$

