In a long-term open-label safety study (Study S187-3-004) conducted over 54 weeks with 324 subjects, a clinically meaningful reduction in "Off" time was apparent by Week 4 and persisted to the Week 54 endpoint. All of the reduction in "Off" time (4.44 hours, P < 0.001) was accompanied by an increase in "On" time without troublesome dyskinesia (4.80 hours, P < 0.001), as was observed in the pivotal study. This improvement was achieved with the majority of subjects (> 75%) requiring only levodopa-carbidopa therapy for treating their PD symptoms throughout the study. The most common adverse events ($\geq 10\%$ of subjects) were complication of device insertion (34.9%), abdominal pain (31.2%), procedural pain (20.7%), nausea (16.7%), excessive granulation tissue (16.0%), postoperative wound infection (15.4%), fall (15.1%), constipation (14.5%), insomnia, (13.6%), incision site erythema (13.0%), and urinary tract infection (11.4%). For each of these preferred terms, the adverse events for the majority of subjects were mild to moderate as assessed by the Investigator.

LCIG treatment also has been shown to be effective in controlling troublesome Dyskinesia in patients with advanced Parkinson's disease. Post hoc analyses of patient data from a 12-week, randomized, double-blind study and a 54-week open-label study were performed. Efficacy was assessed in the subgroup of patients defined by at least 1 hour of "on" time with troublesome dyskinesia at baseline as recorded in Parkinson's disease symptom diaries (double blind: n = 11 levodopa-carbidopa intestinal gel, n = 12 oral levodopa-carbidopa; open label: n = 144 levodopa-carbidopa intestinal gel). The changes in "off" time, "on" time with and without troublesome dyskinesia, and the overall safety and tolerability of LCIG were analyzed. Although not significantly different from oral levodopa treatment (P > 0.05) in the double-blind study, levodopa-carbidopa intestinal gel treatment resulted in a reduction from baseline in "On" time with troublesome dyskinesia (mean [standard deviation] hours: baseline = 3.1 [1.7], change

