4.0 Study Objective

The primary objective of this interventional study is to examine the effect of LCIG treatment relative to that of Optimized Medical Treatment (OMT) on dyskinesia as measured by the Unified Dyskinesia Rating Scale (UDysRS) Total Score.

The Secondary objective is to assess the effect of LCIG treatment relative to that of OMT on dyskinesia as measured by PD Diaries, motor symptoms, motor complications, health-related outcome measures, safety and tolerability.

Motor Symptoms/Motor Complications Will Be Measured by:

- Unified Dyskinesia Rating Scale (UDysRS)
- Parkinson's Disease Diary (PD Diary): normalized average daily hours of OFF time, ON time with troublesome dyskinesia, ON time without troublesome dyskinesia
- Unified Parkinson's Disease Rating Scale (UPDRS) Part III
- Modified Abnormal Involuntary Movement Scale (mAIMS)

Health Related Outcomes Will Be Measured by:

- UPDRS Part II
- Parkinson's Disease Questionaire-8 (PDQ-8)
- King's PD Pain Scale
- Clinical Global Impression of Severity (CGI-S)
- Clinical Global Impression of Change (CGI-C)

Safety and Tolerability Will Be Assessed by:

Adverse event monitoring

EudraCT 2016-001403-23

- Neurological exams
- Clinical laboratory evaluations
- Electrocardiogram
- Vital signs and weight
- Columbia Suicide Severity Rating Scale (C-SSRS)
- Minnesota Impulsive Disorders Interview (MIDI)
- Sleep Attacks Questionnaire (SAQ)

Investigational Plan 5.0

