8.1.3.2 **Secondary Efficacy Analysis**

The secondary efficacy variables are the mean change from baseline to Week 12 in the following measures:

- "ON" time without troublesome dyskinesia as measured by the PD Diary
- Parkinson's Disease Questionaire-8 (PDQ-8) summary index
- Clinical Global Impression of Change (CGI-C) Score
- UPDRS Part II Score
- "OFF" time as measured by the PD Diary
- UPDRS Part III Score

Each secondary efficacy variable will be analyzed with the same MMRM model as the primary analysis. PD Diary variables will be normalized to a 16 hour awake time and the time recorded by the subject on the 3 diaries completed prior to each visit will be averaged.

If the primary efficacy variable is statistically significant, each of the secondary variables will be tested using the fixed sequence above as a gatekeeping procedure and at α level of 0.050. Testing will cease at the point that a secondary variable fails to demonstrate statistical significance.

8.1.3.3 **Additional Efficacy and Health Outcomes Analyses**

Efficacy will also be assessed using the following additional measures:

- UDysRS Historical Score, Objective Score and Parts 1 through 4 Scores
- "ON" time with troublesome dyskinesia and "ON" time without dyskinesia as measured by the PD Diary
- mAIMS

Health outcomes will also be assessed using the following additional measures:

- King's PD Pain Scale
- Percentage (%) of CGI-C responders (response of "minimally improved," "much improved" or "very much improved")

Continuous endpoints will be analyzed with the same MMRM model as the primary analysis. Categorical endpoints will be analyzed with a Fisher's exact test.

Missing data are expected to occur at random and to be largely due to co-morbidities in this advanced Parkinson's disease population. To evaluate this assumption, the MMRM analysis of the primary and secondary variables will be repeated using only subjects who completed the planned treatment period and additional sensitivity analyses to evaluate the

impact of missing data on the primary efficacy results will be performed. These sensitivity analyses will be described in the Statistical Analysis Plan (SAP).

8.1.4 **Safety Analysis**

All safety analysis will be performed on the safety dataset unless otherwise specified. Comparisons between LCIG treatment and OMT groups will be performed with twosided test at the significance level of 0.05.

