9.4 Calculation of Efficacy and Health Outcome Variable

The primary and secondary efficacy variables derived from the above measures are presented in Table 1.

Primary and Secondary Efficacy Variables, and Derivations Table 1.

Instrument	Efficacy Variable	Derivation	Range/Direction
UDysRS: 26 questions, Part 1 (Questions 1 – 11),	Part 1 score	Sum of Questions 1 – 11	0 – 44/lower value desirable
Part 2 (Questions $12 - 15$), Part 3 (Questions $16 - 22$), and Part 4 (Questions $23 - 26$) All questions are	Part 2 score	Sum of Questions $12 - 15$	0 - 16/lower value desirable
5-point (0 – 4). There is no imputation of missing	Part 3 score	Sum of Questions 16 – 22	0 - 28/lower value desirable
responses. If one or more item scores are missing, the	Part 4 score	Sum of Questions 23 – 26	0 - 16/lower value desirable
total score and respective domain score will not be calculated.	Historical score	Sum of Part 1 score and Part 2 score	0 – 60/lower value desirable
	Objective score	Sum of Part 3 score and Part 4 score	0 - 44/lower value desirable
	Total score	Sum of Part 1, Part 2, Part 3, and Part 4 scores	0 - 104/lower value desirable
PD Diary: 48 entries each diary day starting at 6:00 am and goes thru 6:00 am on the following chronological day, each represents 0.5 hour. Subjects were instructed	Normalized "ON" time without troublesome dyskinesia	(Absolute "On" time without dyskinesia + Absolute "On" time with non-troublesome dyskinesia)/Daily awake time * 16	0 – 16 hours/higher value desirable
to record whether "Asleep," "Off," "On without Averimenta ""On with non-tranhecome dvskimesia" or	Normalized "OFF" time	Absolute "Off" time/Daily awake time * 16	0 – 16 hours/lower value desirable
The provided structure of the provided stru	Normalized "ON" time with troublesome dyskinesia	Absolute "On" time with troublesome dyskinesia/Daily awake time * 16	0 – 16 hours/lower value desirable
without dyskinesia," "On with non-troublesome dyskinesia" or "On with troublesome dyskinesia."	Normalized "ON" time without dyskinesia	Absolute "On" time without dyskinesia/Daily awake time * 16	0 - 16 hours/higher value desirable
The "Off" and various "On" times are normalized to 16-hour awake period based a typical person's day.			
Only diaries with at least 12 hours of daily awake time will be considered valid and used in the analysis.			

30

Primary and Secondary Efficacy Variables, and Derivations (Continued) Table 1.

Instrument	Efficacy Variable	Derivation	Range/Direction

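### The diary-dyskinesia part of the secondary objective has no error-controlled test of its own: the first gated secondary mixes troublesome dyskinesia with OFF time, and ON time with troublesome dyskinesia sits outside the sequence

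*Protocol*

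**What the plan says.** Protocol 4.0 states: "The Secondary objective is to assess the effect of LCIG treatment relative to that of OMT on dyskinesia as measured by PD Diaries". The sentence continues with motor symptoms, motor complications, health-related outcomes, safety and tolerability, and SAP 4.1 repeats it. The diary measures listed there, and again in SAP 4.5.1, are "normalized average daily hours of OFF time, ON time with troublesome dyskinesia, ON time without troublesome dyskinesia".

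Protocol 5.3.3.2 then ranks six hierarchical secondaries. First is "ON time without troublesome dyskinesia as measured by the PD Diary". PDQ-8, CGI-C, UPDRS Part II, OFF time and UPDRS Part III follow in that order. Under the additional efficacy endpoints it lists "ON time with troublesome dyskinesia and ON time without dyskinesia as measured by PD Diary".

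Protocol 8.1.3.2 says that after a significant primary result "each of the secondary variables will be tested using the fixed sequence above as a gatekeeping procedure", at 0.050, stopping at the first failure. SAP 6.1, 9.3 and 9.5 say the same. Protocol 8.1.3.3 and SAP 9.3 analyse the continuous additional endpoints with the primary MMRM, outside the multiplicity procedure.

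SAP 9.4, Table 1, derives each diary variable as hours in the state divided by daily awake hours, times 16. ON time without troublesome dyskinesia adds the hours with no dyskinesia to the hours with non-troublesome dyskinesia.

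**The concern.** The objectives list three diary measures. The one that records troublesome dyskinesia directly is the one left out of the sequence. The variable placed first carries dyskinesia in its name, but it also rises hour for hour when OFF time falls.

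Protocol 3.0 already reports an OFF-time benefit for LCIG from a controlled pivotal study. What is new here is dyskinesia: Protocol 3.1 says that no prospective controlled data exist on it. A significant first secondary could be taken as diary support for the dyskinesia result when some or most of the gained hours came from OFF time. The plan offers no controlled test that would separate the two.

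**Working it through.** **1. The plan's own figure.** The only power statement is for the primary endpoint: difference 10, SD 12, two-sided 0.050, 27 per group, 85%. A two-sample t-test gives 85.2% at n = 27, and 27/0.9 = 30 per arm, or 60 in total. This reproduces. No diary variable has a stated power.

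**2. The identity.** Let F = OFF, G = ON without troublesome dyskinesia, T = ON with troublesome dyskinesia, all normalised as in SAP Table 1. If awake time is the sum of the waking states, then F + G + T = 16, so

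change in G = −(change in F) − (change in T).

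The subgroup baselines in Protocol 3.0 agree: 5.5 + 7.4 + 3.1 = 16.0 h. The identity is exact for each diary. It is only approximate for LS means from separate models, because each model has its own baseline covariate.

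**3. The protocol's historical figures (Section 3.0).**
- Pivotal study, between-group: G "LS Mean difference = 1.86 hours, P = 0.0059"; F −1.91 h. Implied T = −(1.86 − 1.91) = +0.05 h.
- 54-week open-label study, within-group: G +4.80 h, F −4.44 h. Implied T = −(4.80 − 4.44) = −0.36 h; 4.44/4.80 = 92.5% of the gain matches OFF.
- Post hoc subgroup with at least 1 h of troublesome dyskinesia (LCIG arm, n = 11, within-arm): G +4.4, F −2.7, T −1.8 h. Sum = −0.1 h, which is rounding. OFF share 2.7/(2.7 + 1.8) = 60%; T share 40%.

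**4. Can G be significant with no effect on T?** Take T = 0, an OFF effect of 1.91 h and 27 per arm. Power ≈ Φ(1.91/(SD × √(2/27)) − 1.96):

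| SD of change in G (assumed) | Power |
|---|---|
| 2.8 | 71% |
| 3.0 | 65% |
| 3.6 | 50% |
| 4.0 | 42% |

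The SDs are assumptions around the subgroup values of 2.8 (OFF) and 3.6 (G). These are chances for one test taken alone. They leave out the primary gate, so they are not the probability of a misleading claim in this trial.

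**5. Does the OFF test in fifth place close the gap?** No. Significant results on both G and F are compatible with T falling, unchanged or rising. No pattern of results on those two tests is a test of T.

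**6. Power for T itself.** By the same formula at 27 per arm, a difference of 0.9 h gives 45% (SD 1.8) or 26% (SD 2.5), and 1.8 h gives 96% or 75%. The between-group differences and the SD of 2.5 are assumptions. The documents give only the within-arm change of −1.8 h (SD 1.8).

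**The case against.** The other side is substantial.

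- **Dyskinesia is tested with error control.** The primary is the UDysRS Total Score, and no secondary is tested unless it is significant. An OFF-driven first secondary can therefore enter the formal claims only after a significant dyskinesia result. This stands. A reader might infer that the trial has no controlled test of dyskinesia, or that the secondary objective as a whole cannot be answered with error control. The documents support neither: motor and health-related parts of that objective are in the sequence through OFF time, UPDRS Parts II and III, PDQ-8 and CGI-C.
- **All three components will be seen.** T is prespecified, derived and modelled with the same MMRM. This stands for estimation; it does not supply a controlled test.
- **The first-ranked variable fits the treatment goal**, which combines less OFF time with less disabling dyskinesia. Ranking it first is defensible, and the point here does not ask for it to be moved.
- **The whole-population figures may mislead.** Entry requires a UDysRS Total Score of at least 30 and diary concordance on at least one interval of ON with dyskinesia (Protocol 5.2.1). The 60/40 subgroup split is therefore a closer guide than the pivotal or 54-week figures, although no minimum of troublesome diary hours is set. This stands. A reader might also infer that LCIG had no effect on troublesome dyskinesia in the pivotal study; +0.05 h is the remainder of two separate LS means without a confidence interval and cannot show that.
- **A seventh test may rarely be reached.** As an illustration, with independent tests, 85% power for the primary and 80% for each secondary, 0.85 × 0.8⁶ = 22%. Those 80% values are assumed. The limitation is real.

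**Conclusion.** The point holds for the diary-dyskinesia component of the secondary objective and no further. That component has no separate error-controlled test, and a significant gain in ON time without troublesome dyskinesia cannot by itself establish a fall in troublesome dyskinesia.

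On the most relevant figures in the documents, roughly 60% of such a gain would be OFF time and 40% troublesome dyskinesia. This rests on 11 patients, within one arm, in a post hoc subgroup, so the split in this trial could differ widely. The identity itself assumes only that awake time is the sum of the waking states.

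Neither the primary analysis nor the validity of the six existing tests is affected. No passage says that the first secondary will be presented as diary proof of a dyskinesia effect; the risk is one of interpretation that the plan leaves open. It is a worthwhile, inexpensive improvement of modest gain.

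**What to change.** In Protocol 5.3.3.2 and 8.1.3.2 and SAP 6.1, 9.3 and 9.5, append change from baseline to Week 12 in normalised ON time with troublesome dyskinesia, analysed with the same MMRM, as the seventh test in the fixed sequence. Align the lists in the protocol synopsis. State that any diary claim about dyskinesia rests on this variable, and report OFF time and ON time with and without troublesome dyskinesia side by side, so that the source of the gained hours is visible.

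A seventh place spends no alpha and leaves the six existing tests as they are. No new data or derivation is needed. The costs are an amendment before database lock, with the ethics approval that Protocol 9.1 requires for amendments, and an entry in SAP 12.0, which now records no change from the protocol. If any earlier test fails, the variable stays descriptive. An earlier position would make the test more likely to be reached but would put another gate before the tests behind it; that trade-off is for the sponsor.

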5.3.4 Safety Variables

Safety and tolerability over the course of the study will be assessed by the following measurements:

- Adverse event monitoring
- Neurological exams
- Clinical laboratory evaluations

- Electrocardiogram
- Vital signs and weight
- Columbia Suicide Severity Rating Scale (C-SSRS)
- Minnesota Impulsive Disorders Interview (MIDI)
- Sleep Attacks Questionnaire

Removal of Subjects from Therapy or Assessment 5.4

5.4.1 **Discontinuation of Individual Subjects**

Each subject has the right to withdraw from the study at any time. In addition, the Investigator may discontinue a subject from the study at any time if the Investigator considers it necessary for any reason, including the occurrence of an adverse event or noncompliance with the protocol. Subjects who withdraw from the study will not be replaced.

Subjects may develop adverse events or abnormalities in vital signs, ECGs, physical examinations, neurological examinations or laboratory determinations during their participation in the study. If these occur, the Investigator may discontinue a subject from the study if, in their clinical judgment, continued participation would result in undue risk or further worsening of the condition.

The following adverse events require Premature Discontinuation:

- Subjects who develop a melanoma during the course of the study should be discontinued from participation and referred for appropriate follow-up care
- Subjects who develop impulsive behavior that is clinically significant, in the judgment of the Investigator, should be discontinued from participation in the study and referred for appropriate follow-up care
- As indicated by answering yes to question 4 or 5 on the C-SSRS, subjects should be discontinued from participation in the study and referred for appropriate follow-up care

• Subjects who become pregnant should be discontinued from participation in the study and referred for appropriate follow-up care

In the event that a subject withdraws or is discontinued from the study after they have begun the PEG-J placement procedure, the assessments for an End of Treatment/Week 12 (V8) should be performed as soon as possible.

If a subject is discontinued from the study with an ongoing adverse event or an unresolved laboratory result that is significantly outside of the reference range, the Investigator will attempt to provide follow-up until a satisfactory clinical resolution of the laboratory result or adverse event is achieved.

The Study Termination eCRF must be completed for all subjects who have entered the study (i.e., have signed the Informed Consent). Subjects dropping out prior to randomization will be considered Screen Failures and the reason for Screen Failure will be entered in the eCRF. In case of Premature Discontinuation of the subject after randomization, the primary reason for Premature Discontinuation will be entered in the eCRF.

5.4.2 Removal of the PEG-J (LCIG Treatment Group Only)

For subjects randomized to LCIG treatment, in case of premature discontinuation of the subject or subject not continuing on commercial treatment, after the PEG-J has been placed, the PEG-J should be removed via endoscopy. The PEG-J should not be removed for 10 to 14 days after placement or until the stoma-tract is formed. Institutional standards for follow-up care after removal of the PEG-J should be followed. The tube must be removed endoscopically by a qualified gastroenterologist proceduralist, surgeon or interventional radiologist. Follow-up visit with examination should occur 1 week following the PEG-J removal.

5.4.3 **Discontinuation of Entire Study**

AbbVie may terminate this study prematurely, either in its entirety or at any study site, for reasonable cause provided that written notice is submitted in advance of the intended termination. The Investigator may also terminate the study at his/her site for reasonable cause, after providing written notice to AbbVie in advance of the intended termination. Advance notice is not required by either party if the study is stopped due to safety concerns. If AbbVie terminates the study for safety reasons, AbbVie will immediately notify the Investigator by telephone and subsequently provide written instructions for study termination.

5.5 **Treatments**

5.5.1 **Treatments Administered**

Subjects may be randomized to one of two treatment groups, OMT or LCIG treatment.

[figure not shown]
5.5.1.1 OMT

[figure not shown]
Those subjects randomized to OMT, will continue on their current anti-PD medication regimen for the duration of the study. All anti-PD medications and medications to treat dyskinesia must remain stable for the duration of the study unless adjustments are medically indicated. The Investigator will provide the prescription for continued OMT.

If modifications are needed, this should first be discussed with the AbbVie TA MD.

5.5.1.2 **LCIG**

LCIG is supplied as a homogenous suspension of levodopa (20 mg/mL) and carbidopa monohydrate (5 mg/mL) in an aqueous intestinal gel (carboxymethyl cellulose). The intestinal gel is dispensed in a medication cassette reservoir of 100 mL, designed to be connected to a portable subject-operated pump. LCIG infusion is administered over a full 16-hour period each day. At night, after disconnecting the pump, the tubing is flushed with potable water.

The total daily dose of infusion LCIG will be composed of three components: (i) the morning dose, (ii) continuous maintenance infusion dose and (iii) extra doses.

Subject dosing is determined individually. The starting total daily dose of LCIG infusion after placement of the PEG-J tube will be based solely on the daily dose of the oral levodopa component from the tablets of levodopa-immediate (IR) taken immediately prior to NJ (or PEG-J) placement during the 16 hour waking day it was anticipated the subject would be on LCIG therapy. The rate of LCIG infusion is typically within the range of 1 to 10 mL/hour (20 to 200 mg of levodopa/hour) in most instances and runs over a period of 16 consecutive hours. The PEG-J tube should be disconnected from the infusion pump before bedtime and the tube should be flushed with 20 mL potable water (both the gastric and jejunal port).

The timing (time of day, interval) of dosing and specific instructions to subjects about when or how to take the dose will be supplied to the subject. No restrictions are given with relation to the time of LCIG dosing relative to meals.

Initial Dose Titration

The initial infusion will be based on calculations described in this section. Extra doses of LCIG may be administered to address immediate medical need throughout the day during initial titration and should be carefully recorded on the Dose Titration Diary.

The daily LCIG infusion dose may be adjusted based on the subject's response to the previous day's treatment and the amount of, if any of extra LCIG doses required. If both the Investigator and subject are satisfied with the effectiveness of treatment, then no change in the LCIG infusion dose is required. If clinically indicated, changes in the dose either upward or downward can be made to further optimize the subject's treatment response.

If at any time during titration the subject develops severe dyskinesia or other levodopa-related complications, the LCIG infusion can be paused, if judged absolutely necessary by the Investigator, until symptoms improve to a clinically acceptable level.

EudraCT 2016-001403-23

Additionally, if at any time during titration, the subject develops a prolonged "Off" state that is unsafe or causes the subject unacceptable discomfort, rescue oral LC-IR dose can be administered, if judged necessary by the Investigator, until symptoms improve. 35

The continuous dose of LCIG should be adjusted to obtain the optimal clinical response for the individual subject. Optimal clinical response is defined by maximizing the functional "On" time and minimizing the number of "Off" episodes during the day. This optimization also minimizes "On" time with troublesome dyskinesia. This determination is made by the Investigator.

LCIG Infusion

LCIG concentration = 1 mL LCIG contains 20 mg of levodopa and 5 mg carbidopa (20 mg/mL).

[figure not shown]
Morning Dose

[figure not shown]
A morning dose will be administered as a bolus infusion by the pump to rapidly achieve a therapeutic dose level (over approximately 10 to 30 minutes). This morning dose is generally 5 to 10 mL and corresponds to 100 to 200 mg of levodopa.

The total morning dose typically does not exceed 15 mL (300 mg levodopa). Subjects are not administered a full equivalent of their usual oral morning dose of levodopa-carbidopa.

Continuous Maintenance Dose

The Maintenance Dose is adjustable in steps of 2 mg/hour (0.1 mL/hour). The dose should be calculated according to the subject's previous daily intake of levodopa. The continuous maintenance dose is adjusted individually. It is usually kept at 2 to 6 mL/hour (40 to 120 mg levodopa/hour). However, higher doses may be clinically indicated. During the titration period, the continuous dose can be titrated in a step wise fashion that meets the clinical and medical needs of the subject. The continuous maintenance dose is first calculated based on the subject's usual total daily dose minus the morning dose.

During treatment, pump alarms may indicate kinking or knotting of the tube. Additionally there may be a sudden deterioration in treatment response with recurring motor fluctuations due to the distal part of the tube becoming displaced from the upper intestine into the stomach. The location of the tube should be determined radiographically. If necessary, the end of the tube can be repositioned to the proximal small intestine and the new placement confirmed radiographically.

If a problem develops with the LCIG system and the LCIG infusion needs to be temporarily discontinued, the Investigator should then place the subject on a regimen of oral levodopa-IR tablets until the problem is resolved and the LCIG infusion can be resumed the following morning. If the subject is placed on an oral regimen of levodopa IR tablets; the dose prescribed should be based on the dose the subject was receiving just prior to the LCIG infusion interruption and adjust the dose as clinically indicated to stabilize the subject.

Extra LCIG Doses

During initial titration, extra doses may be administered on an hourly basis at the Investigator's discretion based on the subject's response. Subsequently, subjects will be allowed to self-administer additional extra doses of LCIG (at intervals of no less than 2 hours) to address immediate medical needs, such as the rapid deterioration of motor function. Extra doses may be given as required if the subject becomes hypokinetic during the day. If the need for extra doses exceeds 5 times per day, the subject should be instructed to contact the Investigator. The Investigator should then consider the need to increase the subject's continuous daily maintenance infusion dose. After the initial dose setting, fine adjustments of the morning dose, the maintenance dose and extra doses can be made as needed.

Nasojejunal Tube

LCIG is intended for continuous intestinal administration. A temporary nasojejunal tube may be used initially with the infusion pump to determine if the subject responds favorably to this method of treatment and to optimize the dose of LCIG before treatment

with a permanent PEG-J tube is started. Only the NJ sets available through this clinical study should be used with LCIG. The NJ should be inserted by a gastroenterologist proceduralist, surgeon, interventional radiologist or experienced nurse if done via the passive method.

Following the placement of the NJ it will be necessary to perform a radiological check for proper tube placement before initiating LCIG.

Alternatively, subjects may proceed directly to placement of the permanent PEG-J tube and start titration without the NJ test phase if deemed appropriate by the Investigator.

[figure not shown]
Percutaneous Endoscopic Gastrostomy with Jejunal Extension (PEG-J)

LCIG will be administered via the components of the percutaneous endoscopic gastrostomy – with jejunal extension (PEG-J) set. Only the PEG-J sets available through this clinical study should be used with LCIG.

A thorough evaluation of the subject's risk of undergoing the PEG-J procedure will be performed by the Investigator and study gastroenterologist proceduralist, surgeon or interventional radiologist as part of the verification of Inclusion/Exclusion criteria prior to Screen V2. Subjects deemed unsuitable for the PEG-J procedure will not be enrolled in the study.

The study gastroenterologist proceduralist, surgeon or interventional radiologist must take appropriate steps to evaluate and minimize the risk to subjects undergoing the PEG-J procedure including aftercare. Additional evaluations for safety, other than those required by the protocol, are permitted at the Investigator's or Study GIs discretion (i.e., additional lab tests).

Placement of the PEG-J will be performed by a qualified gastroenterologist proceduralist, surgeon or interventional radiologist experienced with the placement of PEG-J tubes. Each study site should have one study designated gastroenterologist proceduralist, surgeon, or interventional radiologist and one backup who has experience with and a

EudraCT 2016-001403-23

thorough knowledge of endoscopy and PEG placement, aspects of PD and neurological patients, placement and maintenance of PEG-J tubes, the LCIG System and any related procedures. They must also participate in study staff guided training or equivalent.

The placement target for the end of the jejunal extension tubing is in the proximal small intestine past the ligament of Treitz. Study site personnel will be trained with regard to the proper care and maintenance of the LCIG Infusion System to ensure that high quality care is provided to each subject.

The use of prophylactic antibiotics is required prior to PEG-J procedure. At minimum, a single dose of a 1st or 3rd generation cephalosporin (or an antibiotic with similar coverage) must be administered approximately 30 minutes prior to the PEG-J procedure.

Following PEG-J placement and, at the discretion of the Investigator, the subject may begin initiation and titration of LCIG infusion. LCIG initiation and titration will be performed in the hospital but may be continued as an outpatient (e.g., at a study site, titration center) with appropriate medical supervision. The Sponsor will ensure the Investigator and site personnel are trained on LCIG initiation and titration.

The gastric port of the PEG-J should not be used for the delivery of nutrition and/or other medications unless judged medically necessary following consultation with the AbbVie TA MD. If determined medically necessary, it is imperative that nutrition and/or other medications are delivered only through the gastric port and not the jejunal port. The gastric port must be properly flushed and maintained as outlined in the provided aftercare procedure instructions for the PEG-J set.

Following the PEG-J placement procedure, aftercare of the PEG-J system will initially be performed by trained study staff. Instruction and confirmation that the subject and/or caregiver have a good understanding of proper stoma aftercare and check of the stoma is required before discharge. To ensure adequate adaptation of the stomach and abdominal walls and to reduce PEG-J infections, the aftercare procedure instructions provided by the

Sponsor must be utilized. During aftercare procedures, it is very important not to turn, rotate or twist the jejunal extension tube.

The gastroenterologist proceduralist, surgeon, interventional radiologist, or their designated qualified personnel will examine the subject's stoma site between 2 to 7 days after PEG-J placement, and will continue to follow the subject's progress as an outpatient.

5.5.2 **Identity of Investigational Product**

The chemical nomenclature for levodopa is (-)-3-(3, 4-dihydroxyphenyl)-L-alanine. The chemical name for carbidopa is (-)-L-α-h-ydrazino-3, 4-dihydroxy-αmethylhydrocinnamic acid monohydrate. Levodopa-carbidopa intestinal gel for upperintestinal infusion is a suspension of levodopa-carbidopa monohydrate (4:1) in an aqueous gel (carboxymethylcellulose).

5.5.2.1 **Investigational Product and Supplies**

Table 6. **Study Drug**

Study Drug	Route of Administration	Manufacturer
100 mL Levodopa (20 mg/mL)-carbidopa monohydrate (5 mg/mL) intestinal gel medication cassette reservoirs	upper-intestinal infusion	Fresenius Kabi for AbbVie

Devices are listed below but are not limited to those alone.

Table 7. Investigational Devices Provided for Delivery of Drug

Devices in LCIG System			
Description	Manufacturer		
Pump CADD Legacy 1400	Smiths Medical		
NJ Tube	AbbVie or Covidien		
Safety Adapter	Vygon		
Extension Tube FR	Vygon		
PEG Tube	AbbVie		
Intestinal Tube	AbbVie		
Y-Adapter for PEG Tube	AbbVie		
Click Adapter for PEG Tube	AbbVie		

The Pump comes in a kit that includes a holster, 2 batteries and an instruction booklet. Should the holster get damaged due to wear and tear, an additional pump bag and/or holster can be provided to the subject.

AbbVie will provide LCIG, devices and ancillaries to the site to initiate LCIG after NJ and/or PEG-J placement.

Any replacement LCIG pumps will be shipped to the Investigator allowing the Investigator to program and dispense the pump directly to the subject.

